1.4 Number of patients with quantitative toxicities. Toxicities will be assessed per CTCAE criteria, and each toxicity will be assigned an adverse event (AE) term according to CTCAE definitions (each AE term = unique representation of a specific event used for medical documentation and scientific analyses), and graded as defined by CTCAE (grade 1 = mild; grade 2 = moderate; grade 3 = severe or significant but not immediately life-threatening; grade 4 = life-threatening; grade 5 = death).

1.5 To evaluate whether candidate single nucleotide polymorphisms (SNPs) relevant to eflornithine (DFMO) efficacy.

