9.0 TOXICITIES TO BE MONITORED AND DOSAGE MODIFICATIONS

9.1 This study will utilize the CTCAE version 4.0 (NCI Common Terminology Criteria for Adverse Events) for toxicity and Serious Adverse Event (SAE) reporting.

9.2 Guidelines for monitoring expected and unexpected symptoms/toxicities are defined below.

All interventions can be dose reduced based on toxicity or participant perceived toxicity. All toxicities are recorded on the Adverse Events Summary Form. All patients who discontinue treatment after randomization will continue to be followed for endoscopy results.

Guidelines for Monitoring of Expected and Unexpected Symptoms/Toxic Events:

- **Grade 0**
No monitoring necessary.
- **Grade 1 and Grade 2**
Monitor as needed until problem has resolved (i.e., Grade 0), stabilized (i.e., remains as Grade 1 or Grade 2), or is otherwise explained. If Grade 1 or Grade 2 symptoms persist, the physician will assess whether study medication is to be discontinued or whether symptom management should be initiated.
- **Grade 3 and Grade 4 Toxicities:**
If any Grade 3 or Grade 4 toxicity occurs, ascertain cause of event and study relatedness. If symptoms are related to the study drug, the dose of the drug should be reduced by 50% as follows:

Study Drug	50% Dose Reduction	Frequency	If toxicity improves to grade 0, 1, or 2
Eflornithine or matched placebo	250 mg (1 tab)	Daily	Continue dosing at 50%

If Grade 3 or 4 toxicity persists at 50% dose level, the patient can be given a 4 week drug holiday. After the 4 week drug holiday, the patient may be re-challenged at the aforementioned 50% dose reduction level for 4 weeks. Patient will be removed from protocol treatment if there is a cumulative delay of study intervention >90 days.

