Generalized linear models with a Gaussian link are used to analyze difference in means of DNA damage (flow cytometry, immunostaining), and histopathology at 18 months. The primary endpoint will be reported in terms of marginal means and their difference (DFMO/placebo) with 95% confidence intervals (95%CI) adjusted for baseline variables (age, gender, etc.) and baseline dependent variable values. Mixed models will be used to analyze secondary endpoints including the longitudinal changes from baseline to 6, 18, and 24 months. Time between measurements will be included in the model so that random slopes for the dependent variable at each point in time and random intercepts for each subject will be initially assumed. Adjusted marginal means and 95%CI will be reported with significance levels. The subgroup analysis will involve entering the subgroup analysis variable into generalized linear mixed models: Negative *H. pylori* status, *H. pylori* positive and treated, and *H. pylori* positive and refused treatment. Marginal means and 95%CI are reported for each subgroup after adjusting for baseline variables and including the main independent variable (treatment). A main effects model and an interaction model will be assessed for the treatment and subgroup variables. Prior experience with all three measurements has shown them to be normally distributed. Comparisons of AEs and SAEs between each of the treatment groups will also be performed using person-times poisson rates, with rates being reported using exact 95% confidence intervals. Lastly, we will examine the interaction of treatment arm and genotype expression with respect to different outcomes. STATA 13 is used for computations.

12.2 Accrual Monitoring. The historical experience for patient recruitment is approximately 150 patients per year. The estimated 10% dropout rate is based on prior studies, with excellent 1-year follow-up of >93% at these same study sites.[59,60] The general populations are keenly aware of the impact of gastric cancer in their regions, and the need for prevention. We anticipate balanced recruitment between the two study sites, 150 subjects per site, but with a flexible recruitment strategy. The enrollment at each individual site will be capped at 240 (80%).

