15.3 VICC Multi-Institutional Coordinating Center

The trial additionally will be monitored by the VICC Multi-Institutional Coordinating Center. The actual frequency of monitoring will depend on the enrollment rate and performance of the site. Monitoring will be conducted through onsite and remote monitoring, teleconferences with the Investigator and site staff, and appropriate communications by mail, fax, email, or telephone. The purpose of monitoring is to ensure that the study is conducted in compliance with the protocol, standard operating procedures (SOPs), and other written instructions, and to ensure the quality and integrity of the data.

During scheduled monitoring visits, investigators and the investigational site staff must be available to discuss the progress of the trial, make necessary corrections to case report form entries, respond to data clarification requests, provide required regulatory documents, and respond to any other trial-related inquiries of the monitor. In addition to the above, the Sponsor, CPP, and the FDA may review the conduct or results of the study at the investigational site.

15.3 Adverse Event Reporting Purpose.

Adverse event data collection and reporting, which are required as part of every clinical trial, are done to ensure the safety of patients enrolled in the studies as well as those who will enroll in future studies using similar agents. Adverse events are reported in a routine manner at scheduled times during a trial. Certain adverse events must be reported in an expedited manner. Adverse events should be reported from the start of study drug through 30 days after the last dose of study treatment.

Any event that occurs more than 30 days after the last dose of study agent and is attributed (possible, probable, or definite) to the study agent(s) must be reported according to the instructions outlined in section 15.

15.4 Adverse Event Definitions.

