15.5.1 General Considerations

Investigators should use correct medical terminology/concepts when reporting AEs or SAEs, and avoid colloquialisms and abbreviations. If known at the time of reporting, a diagnosis should be reported rather than individual signs and symptoms (e.g. record only liver failure or hepatitis rather than jaundice, asterixis, and elevated transaminases). However, if a constellation of signs and/or symptoms cannot be medically characterized as a single diagnosis or syndrome at the time of reporting, it is acceptable to report the information that is currently available. If a diagnosis is subsequently established, it should be reported as follow-up information.

All deaths that occur during the protocol-specified AE reporting period, regardless of attribution, will be reported to the appropriate parties. When recording a death, the event or condition that caused or contributed to the fatal outcome should be reported as the single medical concept. If the cause of death is unknown and cannot be ascertained at the time of reporting, report "Unexplained Death." Deaths that occur during the protocol specified adverse event reporting period that are attributed by the investigator solely to progression of disease should be recorded only in the study eCRF and not reported as an SAE.

A pre-existing medical condition is one that is present prior to initiation of protocol specified treatment. Such conditions should be reported as medical and surgical history. A pre-existing medical condition should be re-assessed throughout the trial and reported as an AE or SAE only if the frequency, severity, or character of the condition worsens during the study. When reporting such events, it is important to convey the concept that the pre-existing condition has changed by including applicable descriptors (e.g., "more frequent headaches").

Any AE that results in hospitalization or prolonged hospitalization should be documented and reported as an SAE. If a patient is hospitalized to undergo a medical or surgical procedure as a result of an AE, the event responsible for the procedure, not the procedure itself, should be reported as the SAE. For example, if a patient is hospitalized to undergo coronary bypass surgery, record the heart condition that necessitated the bypass as the SAE.

Hospitalizations for the following reasons do not require reporting:

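### Section 12.1 compares AEs between arms only by person-time Poisson rates, with numerator and person-time undefined; exact limits are too narrow if total AEs are counted and cluster within patients

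*Combined protocol and SAP*

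**What the plan says.** Objective 1.4, repeated as 11.4, defines the toxicity endpoint as "Number of patients with quantitative toxicities", each toxicity being given a CTCAE term and grade. The unit is the patient.

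Section 12.1 covers the analysis in one sentence: "Comparisons of AEs and SAEs between each of the treatment groups will also be performed using person-times poisson rates". On precision, that sentence adds only this: "with rates being reported using exact 95% confidence intervals". No other between-arm AE analysis appears in the document. The sentence does not say whether every event or only each patient's first is counted, whether terms are pooled, which time at risk is the denominator, or which test or interval applies to the comparison itself. The exact limits attach to the rates.

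Four other places bear on this:

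- Section 9.2: "All toxicities are recorded on the Adverse Events Summary Form".
- Section 15.5.1 prefers one diagnosis to a list of symptoms, but accepts separate entries "if a constellation of signs and/or symptoms cannot be medically characterized as a single diagnosis or syndrome at the time of reporting".
- The second section numbered 15.3, on adverse event reporting: "Adverse events should be reported from the start of study drug through 30 days after the last dose of study treatment". Later events are reported only if attributed to the agent.
- The study calendar (section 10.0) marks toxicity notation at Months 21 and 24. Section 9.2 adds: "All patients who discontinue treatment after randomization will continue to be followed for endoscopy results".

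**The concern.** An exact Poisson interval treats each recorded event as independent and every patient as equally prone to events. Total AE counts seldom behave that way: some patients report much more than others, and one episode can give several entries. The variance of the total then exceeds its mean, and the interval is too short by the square root of that ratio. An arm difference in total AEs could be reported with more confidence than the data carry.

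An event rate also does not answer the question the objective asks. Sixty events in 60 of 150 patients and sixty events in 20 of 150 give the same rate for the same person-time, but patient proportions of 40% and 13%.

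Finally, with person-time undefined, numerator and denominator could come from different windows. If they did and early stopping differed by arm, the arm with more stopping would look safer than it is.

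**Working it through.** The plan states no AE rate, dispersion or AE power, so there is no figure of its own to reproduce.

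**Inputs.** From the document: 150 patients per arm (12.1), 18 months on drug plus 6 months off, AE reporting to 30 days (0.99 month) after the last dose. The mean number of events per patient is anchored on section 3.1, reading its percentages as patients. The six common effects sum to 9.0 + 7.5 + 6.5 + 5.6 + 4.3 + 4.7 = 37.6%. Six less common effects at 2-3% and fifteen rare ones at 1-2% bring the sum to 64.6-85.6%, or 0.65-0.86 events per patient; a mean of 2 was also run. The variance/mean ratio V is assumed.

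**Pooled AEs.** If counts have variance V times the mean, coverage of a nominal 95% Poisson interval is approximately 2Φ(1.96/√V) − 1. This gives 92.6%, 89.0%, 83.4% and 74.2% at V = 1.2, 1.5, 2 and 3. Simulation with gamma-Poisson counts, exact limits, equal true rates and equal exposure agrees. Because 12.1 names no test, the type I error column uses the exact conditional test of two Poisson totals as a stand-in.

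| V (assumed) | Coverage of exact 95% limits | Type I error, conditional test |
|---|---|---|
| 1 | about 95% | 4-5% |
| 1.2 | 93-94% | 6-7% |
| 1.5 | 89-90% | 10% |
| 2 | 84% | 15-16% |
| 3 | 74-76% | about 24% |

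Patient-level robust variance gives 5-6% type I error on such data.

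For scale, if episodes are Poisson and each gives m entries, V = E[m²]/E[m]. One episode in three giving two entries gives 2/(4/3) = 1.5. One in ten giving three gives 1.8/1.2 = 1.5.

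**Where it does not bite.** For rare events (0.02 to 0.05 per patient), with between-patient frailty variance up to 2, coverage is 94.8-98.8% and type I error 1.2-3.5%. For single terms at section 3.1 frequencies (0.043-0.09 per patient), V of 1 to 1.2 gives 94-98% coverage and 3-5% type I error; only strong clustering (V = 2) brings coverage down to 86-90%.

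**Person-time.** At 150 per arm with no dropout, 18 months is 225 patient-years, 18 months plus 30 days about 237, and 24 months 300, so the last two differ by 26%. Suppose events come from the section 15.3 window but everyone is given 24 months. The expected rate ratio under equal true rates is then the ratio of mean collection windows: 18.99 months for completers, stopping month + 0.99 for stoppers. Stopping patterns are assumed.

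- 10% v 10%: 1.000
- 15% v 10% at Month 9: 17.64/18.09 = 0.975
- 20% v 10% at Month 9: 17.19/18.09 = 0.950
- 20% v 10% at Month 3: 15.99/17.49 = 0.914

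With matched windows the ratio is 1.00 throughout.

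**Patient proportions.** These ignore exposure. At 0.65 events per completer and 20% v 10% stopping at Month 3, a completer has an event with probability 1 − exp(−0.65) = 0.478 and a stopper with 1 − exp(−0.65 × 3.99/18.99) = 0.128. The arm proportions are 0.8 × 0.478 + 0.2 × 0.128 = 0.408 and 0.9 × 0.478 + 0.1 × 0.128 = 0.443, a ratio of 0.92 under equal true rates.

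**The case against.** The case for leaving 12.1 alone has force. It does not say that AEs are pooled or that repeat events count; objective 11.4 works by CTCAE term, and at term level or with first-event counting the Poisson method performs adequately. Section 15.5.1 makes a single diagnosis the rule and separate symptoms the exception, and section 15.4.1 restricts which laboratory abnormalities count as AEs. The dispersion values are assumed, and at V = 1.2 the loss is small. All of this stands, and it limits the point to total-event counts. It does not remove it: 12.1 refers to AEs without qualification and all toxicities are recorded, so total events is the natural reading, and nothing in the text provides for clustering.

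A reader might infer four stronger things that the documents do not support:

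- **That 12.1 contradicts the objective.** Objectives 1.1 to 1.3 speak of a difference; 1.4 and 11.4 speak only of a number of patients. A descriptive count meets that wording, so this is an omission from the analysis section and not a conflict.
- **That the trial will have an inflated false-positive rate for safety.** No AE test or AE alpha is stated. The type I figures describe a test the plan might use; the coverage figures concern what it does plan.
- **That the rate comparison is biased.** Bias needs both a mismatched denominator and unequal stopping, and the plan specifies neither.
- **That patient proportions should replace the rates.** Proportions ignore exposure and, in the same stopping scenario, are off by about as much (0.92) as a mismatched rate (0.91).

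**Conclusion.** The point holds in a limited form. It is certain from the text that person-time Poisson rates are the only between-arm AE comparison, that numerator, person-time and test are undefined, that no patient-level table is planned in 12.1 for 11.4, and that the AE reporting window and the calendar's toxicity row do not match.

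The under-coverage is conditional on counting total events and on the assumed dispersion: slight at a variance/mean ratio of 1.2, material from 1.5 upwards. It does not extend to rare SAEs, first-event rates or single terms without strong clustering. The person-time bias is conditional on mismatched windows and unequal stopping, and is at most about 9% in the scenarios tried.

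Severity is minor: this is a secondary safety summary, and the primary endpoint and sample size are untouched.

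**What to change.** Amend 12.1 as follows.

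1. As the analysis of 11.4, report by arm the number and percent of patients with at least one event, by CTCAE term and worst grade, with exact confidence intervals. Place this alongside the exposure-adjusted rates and not in their place.
2. Keep total-event rates, but take their intervals and the between-arm rate ratio from negative binomial regression, or from Poisson regression with patient-clustered robust variance, with a log-exposure offset. Keep exact limits for rare SAEs and first-event rates.
3. State whether the numerator is all events or first events, and set person-time to the window in which AEs are collected. Reconcile the section 15.3 reporting window with the toxicity notation at Months 21 and 24 in the calendar.

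The cost is a few sentences and one more table. Total-event intervals widen by √V: about 1.1, 1.2, 1.4 and 1.7 times at ratios of 1.2, 1.5, 2 and 3. As an illustration, 300 events in 225 patient-years is 133 per 100 patient-years with exact limits 119 to 149; at a ratio of 3 the limits would be about 107 to 159.

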13.0 SPECIAL INSTRUCTIONS

13.1 Collection of blood, tissue and stool specimens for biobanking is optional for patients.

The study sites will seek additional patient consent to bank blood, tissue and stool for future translational medicine studies (including genotyping and biochemical assays). This is the established research protocol at the study sites.

14.0 ETHICAL AND REGULATORY CONSIDERATIONS

14.1 Components of sound research practice:

Informed Consent.

The principles of informed consent are described by the U.S. Federal Regulatory Guidelines (Federal Register Vol. 46, No. 17, January 27, 1981, part 50) and the Office for Protection from Research Risks Reports: Protection of Human Subjects (Code of Federal Regulations 45 CFR 46). They must be followed to comply with FDA regulations for the conduct and monitoring of clinical investigations.

Patient Confidentiality.

Confidentiality of patient's personal data will be protected in accordance with the Health Insurance Portability and Accountability Act of 1996 (HIPPA) and national data protection laws, as applicable. HIPPA regulations require that, in order to participate in the trial, a patient must sign an authorization from the trial that he or she has been informed of the following:

- What protected health information (PHI) will be collected from patients in this trial;
- Who will have access to that information and why;
- Who will use or disclose that information;
- That health information may be further disclosed by the recipients of the information, and that if the information is disclosed the information may no longer be protected by federal or state privacy laws;
- The information collected about the research trial will be kept separate from the patient's medical records, but the patient will be able to obtain the research records after the conclusion of the trial;
- Whether the authorization contains an expiration date; and
- The rights of a research patient to revoke his or her authorization.

In the event that a patient revokes authorization to collect or use his or her PHI, the investigator, by regulation, retains the ability to use all information collected prior to the revocation of patient authorization. For patients that have revoked authorization to collect or use PHI, attempts should be made to obtain permission to collect at least vital status (i.e., that the patient is alive) at the end of their scheduled trial period.

In compliance with ICH GCP guidelines and applicable parts of 21 CFR it is a requirement that the investigator and institution permit authorized representatives of Sponsor, the regulatory authorities and the IRB direct access to review the patient's original medical records at the site for verification of trial-related procedures and data.

The investigator agrees to keep all information provided by this study in strict confidence and to request similar confidentiality from his/her staff and the IRB/IEC/REB. Study documents provided (protocols, investigators' brochures, CRFs and other material) will be stored appropriately to ensure their confidentiality.

Patient medical information obtained by this study is confidential, and disclosure to third parties other than those noted in the informed consent form is prohibited. Upon the patient's permission, medical information may be given to his or her personal physician or other appropriate medical personnel responsible for his or her welfare. This medical information must be made available to the IRB and DSMC, upon request, for source verification of study documentation. Data generated by this study must be available for inspection upon request by representatives of the U.S. FDA, local health authorities, the Study Chair and his authorized representative(s), collaborators and licensees, and the IRB for each study site, if appropriate.

All reasonable efforts will be made to keep patient's PHI private and confidential. PHI will only be utilized or relinquished according to U.S. federal privacy guidelines. There are many safeguards in place to prevent the unintentional disclosure of information obtained for or produced by this study. Research data, including the data collected from the medical charts will be entered into a password-protected database. Any publications or public disclosure of data relating to the patient's tumor will be done without any identifying information.~

Confidentiality and security will be maintained for the biospecimen collection within this study. All research biospecimens obtained for this study will be assigned a code and this code used to identify the sample. The samples will not be labeled with the patient's name, address or other information that would identify them. All information will be coded to maintain privacy. Research data, including the data collected from the medical charts will be entered into a password-protected database.

Institutional Review. This study must be approved by an appropriate institutional review committee or ethics committee as defined by Federal Regulatory Guidelines (Ref. Federal Register Vol. 46, No. 17, January 27, 1981, part 56) and the Office for Protection from Research Risks Reports: Protection of Human Subjects (Code of Federal Regulations 45 CFR 46).

Drug Accountability. An investigator is required to maintain adequate records of the disposition of investigational drugs according to procedures and requirements governing the use of investigational new drugs as described in the Code of Federal Regulations 21 CFR 312.

Study Monitoring. This study will be monitored by the VICC Clinical Trials Shared Resource (CTSR). Details are provided in section 15.3.

Study Confidentiality. Please note that the information contained in this protocol is considered confidential and should not be used or shared beyond the purposes of completing protocol requirements unless permission is obtained.

14.2 Record Retention and Documentation of the Trial.

